APPENDIX C

Pill Diary for IRB #12-124 A(5): A Phase 2 Trial of Adjuvant Dabrafenib (GSK2118436) in Patients with Surgically Resected AJCC Stage IIIC Melanoma Characterized by a *BRAF*^{V600E}K Mutation

Number of Pills Given: Pill Bottle(s) returned: Circle **Yes** or **No**
 Total Daily Dose: Number of Pills returned: _____
 (To be completed by RN)

PLEASE FILL OUT AND BRING THIS SHEET AT YOUR NEXT VISIT.

SPECIAL INSTRUCTION: DABRAFENIB is made as a 50 and 75 mg capsules. Your study doctor will give you instruction on the number of pills you will take twice a day. The doses should be taken about 12 hours apart. Taking the medication twice a day for four weeks is one complete cycle. If you forget to take a dose, you should take the dose as soon as possible. The next dose can then be taken at its regularly scheduled time as long as it is at least 6 hours from the last dose. You must not eat anything for 1 hour before you take the medicine or for 2 hours after you take the medicine. If you vomit after you have taken the study medication, **do not** take an additional dose before your next scheduled dose. Please bring this completed log and any unused pill to each appointment.

CYCLE#: _____ **# of WEEK** _____

DAY	MEDICATION	DATE	TIME		NUMBER of 50 mg tablets taken	NUMBER of 75 mg tablets taken
Example	DABRAFENIB	01/01/2010	9:00	AM	3	
	DABRAFENIB		9:00	PM	3	
Day 1	DABRAFENIB			AM		
	DABRAFENIB			PM		
Day 2	DABRAFENIB			AM		
	DABRAFENIB			PM		
Day 3	DABRAFENIB			AM		
	DABRAFENIB			PM		
Day 4	DABRAFENIB			AM		
	DABRAFENIB			PM		
Day 5	DABRAFENIB			AM		
	DABRAFENIB			PM		
Day 6	DABRAFENIB			AM		
	DABRAFENIB			PM		
Day 7	DABRAFENIB			AM		
	DABRAFENIB			PM		
Day 8	DABRAFENIB			AM		
	DABRAFENIB			PM		

Day 9	DABRAFENIB			AM		
	DABRAFENIB			PM		
Day 10	DABRAFENIB			AM		
	DABRAFENIB			PM		
Day 11	DABRAFENIB			AM		
	DABRAFENIB			PM		
Day 12	DABRAFENIB			AM		
	DABRAFENIB			PM		
Day 13	DABRAFENIB			AM		
	DABRAFENIB			PM		
Day 14	DABRAFENIB			AM		
	DABRAFENIB			PM		
Day 15	DABRAFENIB			AM		
	DABRAFENIB			PM		
Day 16	DABRAFENIB			AM		
	DABRAFENIB			PM		
Day 17	DABRAFENIB			AM		
	DABRAFENIB			PM		
Day 18	DABRAFENIB			AM		
	DABRAFENIB			PM		
Day 19	DABRAFENIB			AM		
	DABRAFENIB			PM		
Day 20	DABRAFENIB			AM		
	DABRAFENIB			PM		
Day 21	DABRAFENIB			AM		
	DABRAFENIB			PM		
Day 22	DABRAFENIB			AM		
	DABRAFENIB			PM		
Day 23	DABRAFENIB			AM		
	DABRAFENIB			PM		
Day 24	DABRAFENIB			AM		
	DABRAFENIB			PM		
Day 25	DABRAFENIB			AM		
	DABRAFENIB			PM		
Day 26	DABRAFENIB			AM		
	DABRAFENIB			PM		
Day 27	DABRAFENIB			AM		
	DABRAFENIB			PM		
Day 28	DABRAFENIB			AM		
	DABRAFENIB			PM		

Patient Signature: _____

Date: _____

Consenting Professional Signature: _____

Date: _____

Consenting Professional Comments: _____

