5.3 Administration of Dabrafenib

Dabrafenib will be dosed at 150 mg twice a day by mouth. Patients are instructed to take 150 mg in the morning and 150 mg in the evening, approximately 12 hours apart. Dabrafenib should be administered under fasting conditions, either 1 hour before or 2 hours after a meal. If a study participant vomits after a dose, the patient should be instructed not to retake the dose and should take the next dose at its scheduled time. If a dose is missed, it can be taken up to 6 hours prior to the next dose to maintain the twice daily regimen. Instructions for dose modifications can be found in Section 9.

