9.0 TREATMENT/INTERVENTION PLAN

9.1 Adjuvant Dabrafenib

Treatment will be administered on an outpatient basis. Reported adverse events and potential risks are described in Section 11. Appropriate dose modifications for dabrafenib are described below in Section 9.2. No investigational or commercial therapies other than those described below may be administered with the intent to treat the patient's malignancy.

If all eligibility criteria are met, study participants will self-administer dabrafenib by mouth at a dose of 150 mg twice a day. Four weeks of treatment is one full cycle. After each cycle (\pm 5 days) the study participant will be seen in clinic for a complete clinical evaluation as detailed in section 10.0. A pill diary will be provided to the patient and will be reviewed at the completion of each cycle (Appendix C). This will be used to assure compliance with the regimen. In the absence of treatment delays due to adverse event(s), dabrafenib will continue for 4 cycles or until one of the criteria listed in Section 13 apply.

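### Section 5.3 and the pill diary give patients different fasting windows, and different instructions for a dose remembered more than 6 hours late

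*Combined protocol and SAP*

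**What the plan says.** Section 5.3 sets the schedule: "Patients are instructed to take 150 mg in the morning and 150 mg in the evening, approximately 12 hours apart". On food it says "Dabrafenib should be administered under fasting conditions, either 1 hour before or 2 hours after a meal". On missed doses it says "If a dose is missed, it can be taken up to 6 hours prior to the next dose to maintain the twice daily regimen".

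The pill diary in Appendix C gives the patient's version. On food: "You must not eat anything for 1 hour before you take the medicine or for 2 hours after you take the medicine". On missed doses: "If you forget to take a dose, you should take the dose as soon as possible", followed by "The next dose can then be taken at its regularly scheduled time as long as it is at least 6 hours from the last dose".

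Section 9.1 has patients self-administer the drug as outpatients and has the diary reviewed at the end of each cycle. Of the diary it says: "This will be used to assure compliance with the regimen".

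**The concern.** The diary appears meant to restate Section 5.3 for the patient; the instruction on vomiting, for example, is the same in both. The food and missed-dose instructions are not, and no other section reconciles them.

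The diary is a set of written dosing instructions that the patient takes home. At two doses a day for four 28-day cycles, it covers up to 4 × 28 × 2 = 224 doses per patient. That is the number of doses covered, not the number affected.

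The diary is also the compliance tool, and it cannot measure compliance well with a regimen that differs from the one it instructs. A late dose taken as the diary directs would leave a recorded time outside Section 5.3's limit. A meal 1 to 2 h before a dose would leave no trace, because the diary has no field for meals. Section 13 lists inability to comply with treatment requirements as a reason for removal, so a patient should not be handed instructions that can put them outside those requirements.

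**Working it through.** The plan states no figure on this point, so the check compares the two texts and does clock arithmetic. Inputs are the food and missed-dose rules in Section 5.3 and Appendix C, the 12-hour interval in Section 5.3, and the 9:00 AM and 9:00 PM times in the diary's example row.

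**Food window.** Section 5.3 places the dose relative to the meal; the diary places the meal relative to the dose. Converting Section 5.3, with its hours read as minimum gaps:

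- A dose at least 1 h before the following meal means no food for 1 h after the dose.
- A dose at least 2 h after the preceding meal means no food for 2 h before the dose.

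For a 9:00 AM dose:

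- Section 5.3 bars food from 9 − 2 = 7:00 to 9 + 1 = 10:00.
- The diary bars food from 9 − 1 = 8:00 to 9 + 2 = 11:00.
- Both bar food from 8:00 to 10:00, which is 2 h.
- They conflict from 7:00 to 8:00 and from 10:00 to 11:00, 1 h each.

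| Meal time, 9:00 AM dose | Section 5.3 | Diary |
|---|---|---|
| 6:30 | allowed | allowed |
| 7:30 | not allowed | allowed |
| 8:30 | not allowed | not allowed |
| 9:30 | not allowed | not allowed |
| 10:30 | allowed | not allowed |
| 11:30 | allowed | allowed |

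A patient who follows the diary can therefore depart from Section 5.3, but need not.

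**Missed dose.** Let L be the hours by which the dose is late. The time left to the next scheduled dose is 12 − L. Section 5.3 allows the late dose while 12 − L ≥ 6, that is, while L ≤ 6. The diary allows it at any L and keeps the next dose on schedule only if 12 − L ≥ 6. If the diary's 6-hour spacing is kept, the next dose falls at hour max(12, L + 6) after the missed one was due.

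| Hours late (L) | Hours left (12 − L) | Section 5.3 | Diary: late dose | Next dose if 6 h spacing is kept |
|---|---|---|---|---|
| 4 | 8 | take | take | hour 12, on schedule |
| 6 | 6 | take | take | hour 12, on schedule |
| 7 | 5 | do not take | take | hour 13 |
| 8 | 4 | do not take | take | hour 14 |
| 10 | 2 | do not take | take | hour 16 |

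For a forgotten 9:00 AM dose, the Section 5.3 cut-off is 21:00 − 6 h = 15:00. If it is remembered at 17:00 (8 h late), Section 5.3 leaves the patient to take only the 21:00 dose. The diary says to take it at 17:00, which leaves 21 − 17 = 4 h. Its own 6-hour condition then fails for 21:00 and would be met only at 23:00, 2 h off schedule. The diary does not say whether to delay or omit that dose. The conflict runs from 15:00 to 21:00, 6 of the 12 hours.

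**Design figures.** No dosing instruction enters the decision rule. With 23 patients and success at 9 or more, the exact binomial probability of a positive result is 0.078 at a true rate of 24% and 0.911 at 51%. Both are within the plan's 0.10 and 0.10 error limits and unaffected by this point.

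**The case against.** The food-window swap is hard to dispute; the case on the other side is about the missed dose and the consequences.

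First, Section 5.3 never tells the patient to skip a dose. Its wording is permissive and refers to the next dose without calling it the next scheduled dose. On a literal reading, a late dose at 17:00 followed by one at 23:00 keeps the 6-hour gap, and the diary would be incomplete and not contradictory. It is true that skipping is an inference, and that the diary's silence beyond 6 h is partly a gap. But the same sentence gives its purpose as keeping the twice-daily regimen, and a sliding next dose does not fit that. The diary's instruction to take the late dose has no cut-off where Section 5.3 has one, and that is a conflict.

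Second, the language in Section 5.3 is advisory, and nothing in Sections 5.3 or 9.1 defines a mistimed meal or late dose as a protocol deviation. That stands, and no such claim is made here.

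Third, no harm is shown. Both texts protect 1 h on each side of the dose, the frequency of affected doses is unknown, and no exposure effect is documented. That also stands. It limits the weight of the point, but it does not justify leaving patients with instructions that differ from the protocol.

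Fourth, the documents do not settle which text is right. This is correct, and the fix depends on settling it first.

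**Conclusion.** The concern holds on both counts. The fasting windows conflict in two 1-hour bands around every dose, and the missed-dose instructions conflict for the last 6 of the 12 hours between doses. This assumes that the hours in Section 5.3 are minimum gaps, that the interval is 12 h, and that the late-dose limit is measured to the next scheduled dose.

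This is an internal inconsistency in dosing instructions that should be corrected. It is not a flaw in the statistical design. The number of doses affected cannot be derived, since the documents give no frequency of meals 1 to 2 h before a dose or of doses more than 6 h late. They give no size for any effect on exposure. The 24-month relapse-free survival endpoint, the 9-of-23 rule and the error rates are unchanged.

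**What to change.** Check Section 5.3 against the Investigator's Brochure, which Section 5.1 names as the source for pharmacologic detail. If Section 5.3 is confirmed, replace the two diary instructions with:

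- *Do not eat for 2 hours before or 1 hour after each dose.*
- *If fewer than 6 hours remain before your next dose, skip the missed dose and take the next dose at its scheduled time.*

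Then reissue the diary. It would also help to state the skip instruction explicitly in Section 5.3, where it is now only implied. If the Brochure supports the diary instead, correct Section 5.3 to match, and add to the diary what to do when the 6-hour condition fails.

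The cost is a few replaced sentences and, where the diary changes, one reissued patient form. Design, sample size and analysis do not change.
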